4.5 Interim Analysis

The primary analysis for Period A (Week 0 – 16) will be performed when the last subject completes the Week 16 visit. There will not be a modification to trial conduct based on the results of the analysis. Efficacy assessors will remain blinded for the duration of the study.

4.6 Multiplicity Testing Procedures for Type-I Error Control

The statistical comparisons for the two primary efficacy variables and the three ranked secondary variables will be carried out using graphical procedures as shown in [Figure 2](#).

The 2 primary hypotheses are:

- H1: Risankizumab is not different from secukinumab in achieving a PASI 90 response at Week 52.

- H2: Risankizumab is inferior to secukinumab by 12% in achieving a PASI 90 response at Week 16.

[figure not shown]
The second null hypothesis (H2) will be tested with a two-sided type I error 0.0375. If the result is significant ($p\text{-value} < 0.0375$), then the 0.0375 will be passed to the first null hypothesis (H1), which will be tested with a two-sided type I error 0.05. On the other hand, if the result of H2 is not significant ($p\text{-value} \geq 0.0375$), then H1 will be tested with a two-sided type I error 0.0125.

The multiplicity-controlled, ranked key secondary hypotheses are:

- H3: Risankizumab is not different from secukinumab in achieving a PASI 100 response at Week 52.
- H4: Risankizumab is not different from secukinumab in achieving an sPGA 0 or 1 at Week 52.
- H5: Risankizumab is not different from secukinumab in achieving a PASI 75 response at Week 52.

The three null hypotheses of secondary endpoints (H3, H4, and H5) will be tested in a sequential order with initial two-sided type I error of H3 same as that in H1, only when H1 is significant at its two-sided alpha level. The statistically significant results for the comparison in the higher rank of secondary endpoints are necessary to initiate the testing of the next comparison in the lower rank.

The details of using graphical procedures to control family wise type-I error could be found in Bretz, F, Maurer, W, Brannath, W, & Posch, M (2009).³

Figure 2. Graphical Approach for Type-I Error Control

4.7 Missing Data Imputation

Missing data will be imputed using the following methods for the efficacy analyses:

- Non-Responder Imputation (NRI): The NRI analysis will categorize any subject who has missing value at a specific visit as non-responder for that visit. The only exception is when if the subject is a responder both before and after a specific visit window, then the subject will be categorized as a responder for the visit. The NRI will be the primary approach in the analysis of categorical variables.
- Last Observation Carried Forward (LOCF): The LOCF analyses will use the completed evaluation from the previous visit within the particular period for efficacy measures assessed to impute missing data at later visits in the same period. LOCF will be the primary approach in the analysis of continuous variables, and a secondary approach for categorical variables.

- As-observed: The as-observed analysis will not impute values for missing evaluations. As-observed analysis will be the secondary approach in the analysis of continuous variables.
- Multiple Imputation (MI): The MI will be used as a sensitivity approach to impute missing data in primary endpoints.

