4.2 Study Design

4.2.1 Study Design and Design Diagram

This is a Phase 3, global, multicenter, randomized, open-label, efficacy assessor-blinded, active comparator study examining the effect of 150 mg risankizumab versus 300 mg secukinumab in patients with moderate to severe plaque psoriasis who are candidates for systemic therapy. The study is designed to randomize approximately 310 subjects (155 subjects/arm).

[figure not shown]
The study duration will be up to 88 weeks. The study comprises a 30-day Screening Period, a 52-week open-label study period and a 16-week follow-up period. The follow-up period consists of a follow-up phone call 20 weeks after the last dose of study drug. Subjects in France who were randomized to risankizumab will have two additional dosing

visits at Week 52 and Week 64 and a follow-up phone call 20 weeks after the last study drug dose.

For ease of description, Period A refers to Week 0 – 16, and Period B refers to the rest of the study.

Eligible subjects will be randomized to receive risankizumab or secukinumab in a 1:1 ratio as shown below in [Figure 1](#):

- **Treatment A** (risankizumab SC injection): 2 injections of risankizumab 75 mg (150 mg total dosage) received subcutaneously at Weeks 0, 4, and every 12 weeks (q12w) thereafter until at Week 40. Subjects in France who were randomized to risankizumab will have two additional dosing visits at Week 52 and Week 64.
- **Treatment B** (secukinumab SC injection): 2 injections of secukinumab 150 mg (300 mg total dosage) received subcutaneously at Weeks 0, 1, 2, 3, 4, and every 4 weeks (q4w) thereafter until the last dose at Week 48.

Figure 1. Study Schematic**Risankizumab vs. Secukinumab (M16-766)**

The primary analysis for Period A will be performed when the last subject completes the Week 16 visit. There will not be a modification to trial conduct based on the results of the analysis. Efficacy assessors will remain blinded for the duration of the study.

The Primary Analysis for all efficacy endpoints in Period B will be conducted after all continuing subjects have completed Week 52 and all data pertaining to Week 52 are cleaned and when a database lock will occur to enable the analysis.

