4.3.3 Exploratory Efficacy Endpoint

The exploratory endpoints listed below will be analyzed for all visits in which the assessments are performed (other than those already included as primary or secondary endpoints):

- Proportion of subjects achieving $\geq 75\%/90\%/100\%$ reduction from baseline in PASI score (PASI 75/90/100);
- Proportion of subjects achieving sPGA score of clear (0) or almost clear (0 or 1);

- Change and percent change from baseline in PASI and body surface area (BSA).

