4.4 Sample Size Justification

There are two primary null hypotheses:

- Risankizumab is not different from secukinumab in achieving a PASI 90 response at Week 52.
- Risankizumab is inferior to secukinumab by 12% in achieving a PASI 90 response at Week 16.

The two null hypotheses will be tested in graphical procedures as illustrated in Section 4.6 with initial two-sided type I error 0.0125 and 0.0375, respectively.

The assumptions for the secukinumab Week 16 and Week 52 PASI 90 response rates of 69.7% and 60.6%, respectively, are based on weighted average from secukinumab studies SCULPTURE, ERASURE, FIXTURE, JUNCTURE, and CLEAR. The assumptions for

the risankizumab Week 16 and Week 52 PASI 90 response rates of 75.1% and 81.3%, respectively, are based on weighted average from UltiMMA-1 and UltiMMA-2 trials.

The calculation of sample size is based on ADDPLAN software using superiority test and non-inferiority test. The details of the formula can be found in: Wassmer, G (2003)¹ and Farrington, CP and Manning, G (1990).²

The non-inferiority margin was chosen based on the treatment effect of secukinumab versus placebo in PASI 90 response rate at Week 16. A 12% non-inferiority margin preserves 80% of the treatment effect of secukinumab over placebo.

Approximately 310 subjects (155 subjects per treatment group) will provide more than 90% power to detect the difference of risankizumab and secukinumab at Week 52 using a two-sided alpha level of 0.0125, and 90% power to determine the non-inferiority of risankizumab relative to secukinumab using a tolerance limit of 12% and a two-sided alpha level of 0.0375 at Week 16.

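### Does the unnamed period in the SAP's LOCF rule leave subjects without a value after Week 16?

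*SAP*

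**What the plan says.** SAP 4.7 restricts LOCF twice. The analysis "will use the completed evaluation from the previous visit within the particular period for efficacy measures assessed to impute missing data at later visits", so the source must lie inside an unnamed period, and the value may only "impute missing data at later visits in the same period". The same section fixes the role of the method: "LOCF will be the primary approach in the analysis of continuous variables, and a secondary approach for categorical variables". For categorical variables NRI is primary, and for the primary endpoints MI is the named sensitivity approach. As-observed analysis is the secondary approach for continuous variables. SAP 6.1 and Protocol 7.3 both plan an LOCF repeat of the primary comparison; the protocol text has no period restriction.

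SAP 4.2.1 uses the word period in two ways that could apply. It divides the trial into Period A (Weeks 0 to 16) and a remainder: "Period B refers to the rest of the study". It also describes "a 52-week open-label study period and a 16-week follow-up period". Section 4.7 refers to neither.

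The continuous endpoints concerned are in SAP 4.3.3: "Change and percent change from baseline in PASI and body surface area (BSA"), at all visits where they are assessed. SAP 5.1 defines the efficacy population as all randomized subjects. SAP 3.0 and Protocol 7.1 send further analysis conventions to a supplement, which is not among the documents available here.

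**The concern.** Periods A and B are the more natural reading, because only they divide the post-baseline efficacy visits and the two primary analyses are organized by them. Week 16 then belongs to Period A, and nothing makes it the starting value for Period B. A subject with no assessment after Week 16 would have no LOCF value from Week 20 to Week 52, and SAP 4.7 gives no rule for such a subject.

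Three things seem to be at stake. First, LOCF is the primary approach for change in PASI and BSA, so the denominator after Week 16 could fall short of the full randomized population. Second, the LOCF repeat of Week 52 PASI 90 would differ from the NRI analysis in both imputation and population, so a gap between them could not be put down to imputation alone. Third, the two readings give different tables from the same data, which would leave a choice open after the data are seen. The design offers no obvious reason for a break at Week 16: both arms continue their assigned treatment, with no re-randomization or switch.

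**Working it through.** **1. The plan's own figures.** With 155 per arm, the planned Week 52 PASI 90 rates (60.6% secukinumab, 81.3% risankizumab; SAP 4.4) give 94.0% power at two-sided 0.0125, against a stated figure of more than 90%. For Week 16 non-inferiority (69.7% and 75.1%, margin 12%, two-sided 0.0375) the Farrington-Manning calculation gives 91.0%, against a stated 90%. Both reproduce. Under NRI a subject with a missing visit is still counted, so the LOCF rule does not enter either figure.

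**2. What each reading does.**

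| Last assessment | Periods A and B | 52-week period |
|---|---|---|
| After Week 16 | Carried to later visits | Carried to later visits |
| Post-baseline, at or before Week 16 | No value at Weeks 20 to 52 | Carried to Week 52 |
| None after baseline | No post-baseline value to carry | No post-baseline value to carry |

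The readings differ only in the middle row.

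**3. Who is in that row.** Protocol 5.6 keeps subjects who stop study drug in scheduled visits. Those who withdraw consent should have a premature discontinuation visit, preferably within 2 weeks; if it falls after Week 16 it supplies a Period B value. What remains is mainly withdrawals up to about Week 16 and early losses to follow-up. The documents give no count. If the share were 1%, 2%, 5% or 10% of 310, that would be about 3, 6, 16 or 31 subjects.

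**4. Effect of leaving them out.** Let p be the LOCF rate in all randomized subjects (the planned Week 52 rates stand in for it), d the share of an arm with no value after Week 16, and r the responder share among them when last seen. Both d and r are assumptions. The rate after exclusion is (p - d × r)/(1 - d).

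Example, d = 8% secukinumab and 4% risankizumab, r = 0 in both arms: 60.6/0.92 = 65.87 and 81.3/0.96 = 84.69. The difference is 18.82, a shift of -1.88 from 81.3 - 60.6 = 20.70.

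Shift in the difference (percentage points):

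| d (secukinumab/risankizumab) | r = 0, both arms | r = 50%, both arms | r free by arm, 0 to 50% |
|---|---|---|---|
| 5%/3% | -0.68 | +0.41 | -2.22 to +1.96 |
| 8%/4% | -1.88 | +0.38 | -3.97 to +2.47 |
| 3%/3% | +0.64 | +0.64 | -0.91 to +2.19 |
| 3%/5% | +2.40 | +1.32 | -0.23 to +3.95 |

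With the same r in both arms the range is -1.9 to +2.4. Nothing in the documents supports that restriction. Without it the range is about -4.0 to +4.0. Either way the sign is not determined.

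**5. Effect of carrying values across Week 16 instead.** Planned PASI 90 falls by 69.7 - 60.6 = 9.1 points on secukinumab between Weeks 16 and 52 and rises by 81.3 - 75.1 = 6.2 on risankizumab. If those lost would have followed this average course, carrying their Week 16 status changes the difference by -(d_sec × 9.1 + d_ris × 6.2):

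- 5%/3%: -(0.46 + 0.19) = -0.64 after rounding
- 8%/4%: -(0.73 + 0.25) = -0.98
- 3%/3%: -(0.27 + 0.19) = -0.46
- 3%/5%: -(0.27 + 0.31) = -0.58

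Under that assumption, leaving these subjects out keeps the planned 20.7, and carrying them forward is the option that introduces bias.

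**6. Continuous endpoints.** The shift in an arm's mean is d × (mean in retained - mean in excluded). For each 1% of an arm left out and each 10-point gap in percent change in PASI, that is 0.01 × 10 = 0.1 point.

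**The case for a change.** The strongest case for acting is that an undefined word decides who enters an analysis for which LOCF is the primary approach, and that settling it takes one sentence. Protocol 7.3 sets no period limit, so the restriction exists only in the SAP, and fixing it before the Week 52 lock would remove a choice between two tables. A discontinuation visit does not help with losses to follow-up, or when it takes place at or before Week 16.

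The textual part of this stands: section 4.7 does not name its period, and under the A/B reading a small group has no LOCF value after Week 16. The claim that the plan is therefore deficient does not stand. Protocol 7.1 requires the supplement with the detailed conventions to be final before the Period A lock. The handling of an LOCF window is the sort of detail such a supplement holds, so the documents cannot show that the point is still open. The comparison of NRI with LOCF is supportive, and MI is planned beside it for the primary endpoints. The exploratory continuous endpoints have an as-observed analysis as a second look. As for the substantive remedy, limiting the carry-forward avoids taking a value from Week 16 or before across 36 weeks or more. Against that, the rule as written already allows a Week 20 value to be carried 32 weeks. Neither choice is clearly better.

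**Conclusion.** No change to the plan follows. The ambiguity is real, but it is a missing detail that analysts can settle sensibly in the programming conventions, and either reading gives a usable supportive analysis. The number of subjects in each LOCF table will show which reading was used.

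The reach is limited to exploratory change in PASI and BSA after Week 16 and the LOCF repeats of the Week 52 binary endpoints. No confirmatory test, alpha level or power figure depends on it.

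The possible shift in the Week 52 PASI 90 LOCF difference, about -4.0 to +4.0 points, rests wholly on assumed losses of 3% to 8% per arm and assumed responder shares of 0 to 50%. It illustrates what could happen and is not an estimate. Whole-study carry-forward would exchange it for a bias of about -0.5 to -1.0 points if lost subjects would have followed the planned course. Whether to carry values across Week 16 is a fair trade-off for the sponsor. The one thing that could not be checked is whether the supplement already names the period.

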6.0 Efficacy Analysis**6.1 General Considerations**

The Primary Analysis for all efficacy endpoints pertaining to Period A will be conducted after all continuing subjects have completed Week 16 and all data pertaining to Period A are cleaned and a database lock will occur to enable the analysis. This is the one and final efficacy analysis for Period A. The results will be included in an interim clinical study report (CSR) to support the efficacy and safety evaluation in the initial 16 weeks of treatment.

The Primary Analysis for all efficacy endpoints in Period B will be conducted after all continuing subjects have completed Week 52 and all data pertaining to Week 52 are cleaned and when a database lock will occur to enable the analysis.

The efficacy assessors will remain blinded for the duration of the entire study.

The efficacy analysis will be conducted in the ITT Population and Per-protocol Population. The ITT Population will be analyzed by treatment group as randomized. For the Per-protocol Population, subjects will be analyzed as randomized.

Comparison of the primary endpoints will be made between risankizumab group and secukinumab group using the Cochran-Mantel-Haenszel test adjusting for stratification by weight (≤ 100 kg vs. > 100 kg) and prior systemic biologic use for psoriasis. For the primary analysis, Non-Responder Imputation (NRI) will be used. The analysis will be repeated using last observation carried forward (LOCF) and Multiple Imputation (MI).

Categorical variables will be analyzed using Cochran-Mantel-Haenszel (CMH) test, stratified by weight (≤ 100 kg vs. > 100 kg) and prior systemic biologic use for psoriasis.

Continuous variables will be analyzed using ANCOVA method, with treatment, pooled center, and Baseline values in the model.

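### Exploratory PASI and BSA change scores rest on within-period LOCF, backed only by an as-observed analysis; a mixed model would suit the data better and keep subjects who have no Period B value (low severity)

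*SAP*

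**What the plan says.** SAP 4.7 sets the missing-data methods by type of variable.

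- Continuous: "LOCF will be the primary approach in the analysis of continuous variables, and a secondary approach for categorical variables". The fallback is "As-observed analysis will be the secondary approach in the analysis of continuous variables".
- Categorical: "The NRI will be the primary approach in the analysis of categorical variables".
- Multiple imputation: "The MI will be used as a sensitivity approach to impute missing data in primary endpoints". Those endpoints are binary.

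The LOCF rule is limited in time. It uses the "evaluation from the previous visit within the particular period for efficacy measures assessed to impute missing data at later visits in the same period". The periods are defined in SAP 4.2.1 (and Protocol 7.1): "For ease of description, Period A refers to Week 0 – 16, and Period B refers to the rest of the study".

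The model is in SAP 6.1: "Continuous variables will be analyzed using ANCOVA method, with treatment, pooled center, and Baseline values in the model". The continuous efficacy variables are the absolute and percentage changes in PASI and BSA. SAP 4.3.3 lists them as exploratory, for every visit with an assessment. They are not among hypotheses H1 to H5 in SAP 4.6. SAP 5.1 names the ITT Population, meaning everyone randomized, for the efficacy analyses.

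**The concern.** LOCF is a single imputation. It assumes that a subject's value stays constant after the last visit, and the ANCOVA then treats the filled value as a measurement. The bias depends on when subjects leave, and from which arm. Allocation is open to subjects and investigators, so withdrawal could differ by arm.

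The sponsor's own planning rates (Protocol 7.3, SAP 4.4) sit badly with constancy. PASI 90 is assumed to rise on risankizumab and fall on secukinumab between Weeks 16 and 52.

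The same-period limit shortens the carry but opens a gap. A subject last assessed at or before Week 16 has no Period B value to carry to Week 52, and the SAP gives no rule for that subject.

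The as-observed analysis does not make up for either problem. At each visit it drops everyone without a value and ignores their earlier data. At stake are the size and precision of the reported differences in PASI and BSA change, not a confirmatory claim.

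**Working it through.** **1. The plan's own figures.** The only stated results are the powers for the binary primary endpoints with 155 per arm. Both reproduce, and neither concerns the continuous endpoints.

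- Week 52, 60.6% vs 81.3%, two-sided 0.0125. The pooled rate is 0.7095. z = [0.207×√155 − 2.498×√(2×0.7095×0.2905)] / √(0.606×0.394 + 0.813×0.187) = (2.577 − 1.604)/0.625 = 1.56, so power is 94.0%.
- Week 16, 69.7% vs 75.1%, margin 12%, one-sided 0.01875, Farrington-Manning with constrained rates 0.653 and 0.773. z = (0.174 − 2.080×0.0509)/0.0507 = 1.34, so power is 91.0%.

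**2. Longest carry.** The PASI/BSA row of Protocol Appendix D is broken in the available text. I assume that Week 4 is the first post-baseline assessment and Week 20 the first in Period B.

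- Into Week 52: 52 − 20 = 32 weeks. It would be 52 − 16 = 36 if Week 16 counted as Period B, but the definition puts it in Period A.
- Into Week 16: 16 − 4 = 12 weeks, or 16 if a baseline value may be carried.

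**3. Constancy against the planning rates (PASI 90, Week 16 to Week 52).**

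- Risankizumab: 81.3 − 75.1 = +6.2 points.
- Secukinumab: 60.6 − 69.7 = −9.1 points.
- Difference between arms: from 5.4 to 20.7 points.

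These are responder rates, not mean PASI. They suggest drift in opposite directions but do not measure it on the continuous scale.

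**4. Simulated size; all inputs assumed.** 155 per arm. Mean PASI improvement goes from 89% to 93% (risankizumab) and from 89% to 85% (secukinumab) between Weeks 16 and 52, so the true Week 52 difference is 8.0 points. SD 18; visit correlation 0.5 + 0.5×0.9^lag; monotone dropout, either unrelated to outcome or dependent on the previous value; LOCF only from Week 20 on; unadjusted difference in means; 2,500 runs.

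| Dropout, risankizumab/secukinumab | Related to outcome | LOCF bias (coverage) | As-observed bias (coverage) |
|---|---|---|---|
| 5/5% | no | −0.10 (94.2%) | +0.03 (94.6%) |
| 5/5% | yes | −0.12 (95.0%) | +0.02 (94.4%) |
| 7/15% | no | −0.23 (95.3%) | +0.06 (95.4%) |
| 7/15% | yes | −0.39 (94.4%) | −0.75 (92.9%) |
| 10/20% | no | −0.43 (94.8%) | −0.01 (95.4%) |
| 10/20% | yes | −0.63 (93.2%) | −1.05 (90.7%) |
| 15/30% | no | −0.68 (94.2%) | −0.04 (95.3%) |
| 15/30% | yes | −0.96 (92.1%) | −1.55 (88.4%) |

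Hand check of the 15/30% row without outcome dependence. Each arm drifts 4/36 point per week, in opposite directions. Of 12 possible first-missing visits (Weeks 8 to 52), 8 leave a Period B value, with carries of 4 to 32 weeks (mean 18). The carried share of those analysed is about 0.10/0.95 = 0.105 on risankizumab and 0.20/0.90 = 0.222 on secukinumab. Bias ≈ −18×(4/36)×(0.105 + 0.222) = −0.65, against −0.68 simulated.

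**5. Second set; all inputs assumed.** True difference 7.0, SD 17, front-loaded outcome-related dropout, 1,500 runs.

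| Dropout, risankizumab/secukinumab | LOCF bias (coverage) | As-observed bias (coverage) |
|---|---|---|
| 6/14% | −0.3 (94.5%) | −0.7 (94.1%) |
| 10/20% | −0.5 (93.6%) | −0.85 (91.9%) |
| 6/23% | −0.75 (92.6%) | −1.6 (86.8%) |
| 14/6% | +0.1 (96%) | +0.7 (93.5%) |

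A sequential-regression likelihood estimate, standing in for MMRM, had bias within 0.1. Its SD equalled that of LOCF and was about 4-5% below as-observed. Other early-dropout shapes moved the LOCF bias to between −1.1 (6/23%) and +0.4 (14/6%), with coverage of 93-95% except 90.5-93.3% at 6/23%.

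**6. Subjects without a Period B value.** At 6/23%, about 4 risankizumab and 15 secukinumab subjects had none. The Week 52 set is then about 151 and 140 of 155, or 291 of 310.

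**The case against.** The case for leaving the plan alone is substantial.

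- **Low stakes.** The endpoints are exploratory and outside the testing graph. The primary and key secondary endpoints are binary and use NRI. This stands, and it fixes the severity.
- **Few gaps.** Protocol 5.6 keeps subjects who stop study drug in all scheduled visits unless they withdraw consent. Missing values should come mainly from study withdrawal and missed visits. With no dropout rate stated, 23% in one arm is only a scenario. This also stands: at 5/5% the effect is negligible.
- **A second analysis exists.** As-observed is prespecified and is unbiased when dropout is unrelated to outcome. When dropout is outcome-related and unequal, it is usually the worse of the two.
- **The simulation favours the fix.** Dropout was generated as missing at random, the condition under which a likelihood analysis is valid. That is fair, so its near-zero bias is a best case.
- **Details may be elsewhere.** SAP 3.0 refers further conventions to a supplement, which could hold a rule for subjects without Period B data. It is not among the documents reviewed.

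A reader might infer that a Week 4 value can be carried 52 − 4 = 48 weeks to Week 52, so that the steep early fall in PASI distorts the Week 52 result. The same-period rule excludes this. Simulating such unrestricted carry gives about +1.6 to +2.5 points at 6/23% and −1.3 to −1.9 at 14/6%, but that is not the planned method. Nor do the documents support stating bias or under-coverage as established, since they give no dropout rate, SD or trajectory.

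**Conclusion.** The concern holds in a limited form. Within-period LOCF is a weak primary method for the continuous endpoints, its only companion is usually weaker when dropout is unequal and outcome-related, and the Week 52 analysis has no stated rule for subjects without Period B data. Read literally, those subjects fall out of an analysis that SAP 5.1 assigns to the ITT Population.

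Under the assumed inputs (true difference 7 points, SD 17, outcome-related dropout of 6-23% per arm), LOCF bias is roughly −1 to +0.4 points. Coverage is about 92-95%, slightly lower in the most unequal scenario. The complete-data standard error is 17×√(2/155) = 1.93, so a bias of 1 point is about half a standard error. A negative sign understates risankizumab's advantage, and this occurs when secukinumab loses more subjects. The likelihood analysis removes nearly all of the bias in these scenarios but shows no clear precision gain over LOCF.

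Size and direction depend on assumptions that the documents cannot confirm. No primary or key secondary conclusion is affected. Low severity.

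**What to change.** In SAP 4.7 and 6.1, make the primary analysis of continuous endpoints an MMRM on all observed post-baseline visits across both periods. Include treatment, visit, treatment-by-visit, baseline, baseline-by-visit and the remaining covariate of the planned ANCOVA (pooled center). Use an unstructured covariance with a named fallback: with four-weekly assessments from Week 4 to Week 52 there are 13 visits and 13×14/2 = 91 covariance parameters, so non-convergence is possible. Subjects with only Period A data then stay in the model.

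Keep LOCF-ANCOVA as a secondary analysis. State how it treats a subject with no Period B assessment, and report the number of such subjects by arm.

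The cost is SAP text and one standard procedure, with no new data or visits. The drawback is reliance on missing at random, which the data cannot verify. Retaining LOCF also allows comparison with older trials.
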